12.5. Analyses of Pharmacogenomics, Exploratory Biomarkers, and Anti-Drug Antibodies

Analysis of the ADA results is to be determined and may include determination of the subject's positive/negative ADA status at baseline, treatment-emergent ADA in subjects with a negative baseline, as well as a post-baseline increase in titer for subjects with positive ADA at baseline.

Pharmacogenomics, and exploratory biomarkers will be reported separately.

12.6. Analyses of Respiratory Tract Infections

The number and percentage of subjects with any RTI will be provided.

12.7. Interim Analysis

After 50% of Cohort 1 subjects have completed study drug administration and have undergone protocol-specified procedures and assessments for ≥10 days, the Principal Investigator (PI)

and Sponsor will review blinded safety data: AEs (including systemic reactogenicity/injection site reactions, hypersensitivity reactions, and AESIs), vital signs, 12-lead ECGs, and clinical laboratory results (hematology, coagulation, serum chemistry, urinalysis) to determine the safety and tolerability of the study drug. The incidence and severity of AEs, and any adverse changes in vital signs, clinical laboratory findings, and ECGs will be considered when determining safety and tolerability of study drug. If the dose is determined to be safe and well tolerated ≥10 days after dosing, Cohort 2 will be enrolled. Enrollment of the remaining 50% of Cohort 1 will continue while the safety data of the first 50% of Cohort 1 is being reviewed. Similar processes will be followed for dose escalation from Cohort 2 to Cohort 3.

After the final subject of Cohort 2 has completed the Day 90 visit, Cohorts 1 and 2 may be unblinded for a formal interim data analysis. In addition, unblinded data reviews may occur as needed.

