6.2. Criteria for Evaluation

6.2.1. Safety and Tolerability of Study Drug

Safety and tolerability will be assessed by monitoring AEs (including systemic reactogenicity/injection site reactions, hypersensitivity reactions, and AESIs), vital signs, 12-lead ECGs, clinical laboratory results (hematology, coagulation, serum chemistry, urinalysis), and concomitant medication usage throughout the study.

See Section 6.1 for details regarding cohort/dose level enrollment timing and assessment of safety and tolerability for dose escalation decision.

If a dose level is considered not safe or well tolerated, the study drug assignment for the subject(s) with the safety issue may be unblinded. The Sponsor may also independently decide to unblind the entire cohort for safety concerns or terminate enrollment for any reason.

If any subject develops a Grade ≥2 AE or an SAE of any grade that is deemed related to the study drug, the mechanism of the AE may be assessed (i.e., cytokine level, complement activation, immunoglobulin G [IgG] subtypes, immunoglobulin E [IgE], T-cell/B-cell/monocyte and basophil activation as assessed by flow cytometry, ADA development, and immune complex formation) at Sponsor and Investigator discretion, and the study dose may be modified for the remainder of the study.

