6.6. Method of Treatment Assignment and Blinding

After informed consent has been obtained, subjects will be screened for study eligibility before randomization.

Within each dose level (Cohorts 1, 2, and 3), subjects will be randomized to receive a single dose of CD388 Injection or saline placebo (treatment assignment is blinded). The study site's pharmacist (or pharmacist designee) will obtain a computer-generated study drug assignment. A subject is considered randomized when a randomization transaction is appropriately recorded.

Unless a formal interim analysis is conducted after all subjects have completed the Day 90 visit, all blinded study personnel (including the Sponsor, Investigator, and site personnel directly involved in study conduct) and subjects will remain blinded to study drug assignment until the study is completed and the final database is locked with the exception of the unblinded pharmacy personnel, pharmacy monitor, and unblinded Sponsor personnel (such as Data Review Committee, clinical supply manager, PK lead, and quality manager) who may be unblinded to study medication at any time during study conduct. The pharmacy monitor will monitor study drug preparation and accountability during the study and cases in which unblinding is required due to a safety or tolerability issue. To maintain study blinding, study drug preparation will be performed by an unblinded site pharmacist (or qualified unblinded personnel at the study site not involved with study procedures or evaluations). Any unblinding related to an interim analysis will be documented in the blinding plan.

Instructions for study drug preparation and dosing are outlined in the Pharmacy Manual provided separately to the site. In the event of a medical emergency requiring the Investigator to know the identity of the study drug, the Investigator will follow the procedures outlined in Section 8.4.

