6.7. Data Review Committee

A Sponsor Data Review Committee, consisting of representatives of the Sponsor not involved in day-to-day management of the study, may be established to review unblinded data to allow

strategic development decisions within and across development programs. The procedures of the Data Review Committee will be documented in a charter.

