8.4. Breaking the Blind

The study is a double-blind design. The Sponsor, Investigator, study site personnel, and subjects will not make any effort to determine which blinded study drug (CD388 Injection or placebo) is administered. Unblinded pharmacy personnel will be responsible for preparing syringes such that the double-blind is maintained.

Only in the case of an emergency, when knowledge of the study drug is essential for the clinical management or welfare of a specific subject, may the Investigator unblind a subject's study drug assignment.

As soon as possible and without revealing the subject's study drug assignment (unless important to the safety of subjects remaining in the study), the Investigator must notify the Sponsor if the blind is broken for any reason. The Investigator will record in source documentation the date and reason for revealing the blinded study drug assignment for that subject.

As PK samples from subjects assigned to placebo treatment will not be analyzed for determination of CD388 concentrations, the bioanalytical laboratory will receive the randomization list to allow for correct selection of the samples. Unblinding of the randomized treatment assignment will be performed at the bioanalytical laboratory. Specific procedures will be in place to ensure that randomized treatment assignment will not be revealed to anyone involved in the execution of the study.

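### Sections 6.6 and 12.7 set different conditions for interim unblinding, and 12.7 does not say who may receive the codes

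*Protocol*

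**What the plan says.** Three protocol sections govern when assignments may be revealed before the end of the study.

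- **Section 6.6** sets a default and one exception. The exception reads "Unless a formal interim analysis is conducted after all subjects have completed the Day 90 visit, all blinded study personnel". Without it, those personnel (defined to include the Sponsor, the Investigator and site staff running the study) and the subjects "will remain blinded to study drug assignment until the study is completed and the final database is locked". Pharmacy personnel, the pharmacy monitor and certain Sponsor roles stand apart, as people "who may be unblinded to study medication at any time during study conduct".
- **Section 12.7**, describing a formal interim, provides: "After the final subject of Cohort 2 has completed the Day 90 visit, Cohorts 1 and 2 may be unblinded". It adds that other unblinded reviews may take place as the need arises. It does not say who sees the codes or results.
- **Section 6.4** keeps the blinded site and Sponsor team blinded at least until the last subject of a given cohort has had the Day 90 visit.

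Other provisions touch the point. Section 6.6 says "Any unblinding related to an interim analysis will be documented in the blinding plan". Section 6.7 describes a Sponsor Data Review Committee that "may be established to review unblinded data". Section 8.4 allows the Investigator to break the blind in an emergency, "when knowledge of the study drug is essential for the clinical management or welfare of a specific subject". Section 6.2.1 says that, if a dose level is judged not safe or not well tolerated, "the study drug assignment for the subject(s) with the safety issue may be unblinded", and it lets the Sponsor unblind a whole cohort for safety concerns.

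**The concern.** The two sections attach early unblinding to different events. Section 6.6 waits for all three cohorts, while 12.7 waits only for the last Cohort 2 subject. Section 6.6 also releases everyone in its list at once when its condition is met, whereas 12.7 is silent on recipients. A site reading 12.7 with the Day 90 minimum in 6.4 could reasonably conclude that codes for Cohorts 1 and 2 may be given to it. A site reading 6.6 would conclude the opposite.

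What is at stake is the data still being collected after Day 90. The primary endpoint is the incidence and severity of treatment-emergent adverse events. These are counted through the final visit and tabulated by severity and relationship to drug (Section 12.3). The Investigator must judge causality for every event (Section 11.5.1), and the guideline in Table 6 leaves much to judgement. Respiratory infection surveillance runs to the final visit, and a swab is taken only after a subject reports symptoms (Section 6.1). Knowledge of assignment could influence both.

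**Working it through.** No sample size, power or error rate is involved, and the protocol gives no figure to reproduce. The check is a comparison of text followed by timeline arithmetic.

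**Step 1. The rules side by side**

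| | 6.4 | 6.6 | 12.7 |
|---|---|---|---|
| Who must have completed Day 90 | last subject of the cohort concerned | all 27 subjects | last Cohort 2 subject |
| Assignments concerned | that cohort | all | Cohorts 1 and 2: 2 × 9 = 18 |
| Whose blind may be lifted | blinded site and Sponsor team | Sponsor, Investigator, site and subjects together | not stated |

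The rule in 6.4 is a minimum and is compatible with either trigger.

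**Step 2. Can a 12.7 interim satisfy 6.6?** Only if every Cohort 3 subject has also reached Day 90 by then, which 12.7 does not require. Cohort 3 opens after half of Cohort 2 has at least 10 days of data. If all of Cohort 2 were dosed on one day, Cohort 3 would be at about Day 90 − 10 = 80 at most, so the 6.6 condition would not be met. More generally, if the last Cohort 3 dose falls G days after the last Cohort 2 dose, the two trigger dates lie G days apart. The protocol does not give G.

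**Step 3. One interim or two?** The opening of Section 12 requires the SAP to be final before unblinding for the first interim, which suggests that more than one may be planned. Suppose 12.7 describes an earlier interim on Cohorts 1 and 2, and 6.6 a later one on everyone. At the earlier one the 6.6 exception has not been met, so its default holds for everyone in its list. Section 12.7 is then consistent with 6.6 only if its results go to people already allowed to see codes, and 12.7 does not say that.

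**Step 4. Follow-up remaining at each trigger.** Inputs: final visit at Day 120 for Cohort 1 and Day 165 for Cohorts 2 and 3 (Table 1, note a), and the 10-day escalation gates (Section 12.7). Remaining days = final visit day − study day at the trigger.

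| Subject | 12.7 trigger | 6.6 trigger |
|---|---|---|
| Last-dosed Cohort 3 | not covered | 165 − 90 = 75 |
| Last-dosed Cohort 2 | 165 − 90 = 75 | 75 − G, if Cohort 3 is dosed last |
| First half of Cohort 2 | up to 75, fewer if dosed earlier | at most 165 − (90 + 10) = 65 |
| Any Cohort 1 subject | at most 120 − 90 = 30 | at most 120 − 90 = 30 |
| First half of Cohort 1 | at most 120 − (90 + 10) = 20 | at most 120 − (90 + 20) = 10 |

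With assumed G of 14, 28 or 56 days, 75 − G is 61, 47 or 19. The 30-day limit for Cohort 1 under 12.7 relies on 6.4: a Cohort 1 subject dosed after the last Cohort 2 subject must still reach Day 90 before that cohort's codes are released.

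**Step 5. Visit windows.** Day 90 has ±7 days and the final visit ±14. The 75 days become (165 − 14) − (90 + 7) = 54 to (165 + 14) − (90 − 7) = 96. The 30 days become (120 − 14) − (90 + 7) = 9 to (120 + 14) − (90 − 7) = 51.

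These are lengths of time during which ratings could be made with assignment known. They are not estimates of bias.

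**The case against.** The best defence is that 12.7 concerns an analysis, not a release to the site. Day 90 of the last Cohort 2 subject can be read as a data cut, with results going only to the Sponsor's unblinded team, which 6.4 and 6.6 already recognise. Section 8.4 supports this, because it limits the Investigator's own unblinding to emergencies. Recipients may also be named in the blinding plan or the committee charter, which are not shown.

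Much of this stands. A reader might infer that 12.7 orders the site to be unblinded. It does not: unblinding is optional and no recipient is named. A reader might also argue that, because the listed Sponsor roles may see codes at any time, the Day 90 condition must be meant for someone else. That does not follow, since a data cut needs a date whoever reads the results. Nor does the text prove that the two sections describe the same interim.

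Three things remain. The restriction to unblinded Sponsor roles is a sensible reading but is not written in 12.7. A blinding plan that documents unblinding does not settle which of two protocol conditions governs, and the Data Review Committee is optional. And even on the two-interim reading, the 6.6 exception expressly releases the Investigator, site and subjects while some subjects are still short of Day 165.

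**Conclusion.** The point holds as an inconsistency in the protocol that should be corrected before any interim. The 12.7 interim is outside the 6.6 exception whether one interim or two is intended, and 12.7 leaves recipients open. Where the 6.6 exception is used, the protocol itself permits site and subject unblinding while primary-endpoint data are still being collected.

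The largest nominal exposure is 75 days, in the last-dosed Cohort 2 subject under 12.7 or the last-dosed Cohort 3 subject under 6.6. In Cohort 1 it is at most 30. These figures assume visits on their nominal days and that codes reach the Investigator, site or subjects as soon as the trigger is met.

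The consequence is conditional and limited. Dose escalation relies on blinded data. The safety and respiratory infection analyses are descriptive, and the infection endpoint is exploratory. Injection-site inspection, the inpatient stay and the 28-day halt window all end before Day 90. A reader might infer damage to escalation decisions or to an error rate, but the documents support neither: the interim carries no test or stopping boundary. They also do not show which trigger the Sponsor intended.

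**What to change.** 1. Reconcile 6.4, 6.6 and 12.7 so that all three describe the same interim or interims, with the cohorts and Day 90 condition for each, and state that any cohort outside an interim stays blinded. The Sponsor must say which trigger or triggers it intends.
2. Rewrite both the exception in 6.6 and the text of 12.7 so that a formal interim, or any additional unblinded review, releases codes and subject-level results only to the already defined unblinded Sponsor personnel or the Data Review Committee. Changing only the trigger in 6.6 would not do, because its exception would then release the site and subjects earlier.
3. Keep the Investigator, blinded site staff and subjects blinded until final database lock, which is already the 6.6 default, except for unblinding under 8.4 and 6.2.1. Align the Day 90 wording for the clinical site in 6.4 with this.

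The cost is wording in the protocol and the blinding plan, and no release of codes to the site at an interim. The interim analyses themselves can go ahead as planned.

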12.8. Determination of Study Sample Size

A total of 27 subjects will be enrolled in this study, with 21 of these subjects to receive CD388 Injection and 6 to receive placebo. The number of subjects was selected to allow sufficient evaluation of safety and tolerability, and PK, and is consistent with standards of practice for Phase 1 ethnic bridging studies.

12.9. Handling of Dropouts and Missing, Unused, and Spurious Data

Every effort will be made to collect all data at specified times. Handling of missing data will be detailed in the SAP.

12.10. Subject Disposition

Enrollment and discontinuations from the study will be summarized, including the reasons for discontinuation.

12.11. Deviation Reporting

Protocol deviations will be summarized. Protocol deviations are defined as any variation from the protocol, including enrollment of a subject who did not meet all inclusion and exclusion criteria and failure to perform the assessments and procedures within the required time frame.

13. INVESTIGATOR REQUIREMENTS

13.1. Protocol Adherence

The Investigator must adhere to the protocol as detailed in this document and agree that the Sponsor must approve any change to the protocol before seeking approval from the IRB/IEC. The Investigator will be responsible for enrolling only those subjects who have met the study selection criteria.

13.2. Electronic Case Report Forms

The contract research organization will make the eCRF accessible to authorized personnel over the internet from an electronic data capture (EDC) system used for the recording of study data as specified by this protocol. All eCRFs must be completed by trained study personnel. The Investigator is responsible for ensuring that the eCRF data are entered and completed in a timely manner.

Once all data queries and issues have been resolved for each subject, the Investigator will electronically sign each subject's eCRF to attest to the accuracy of the data.

13.3. Source Document Maintenance

Source documents are defined as documentation related to original observations and activities of a clinical investigation. Source documents may include, but are not limited to, study progress notes, study- or subject-specific e-mail correspondence, computer printouts, laboratory data, and recorded data from automated instruments. All source documents produced in this study will be maintained by the Investigator and made available for inspections by the Sponsor and by regulatory authorities. The original signed ICF for each participating subject shall be filed with records kept by the Investigator, and a copy shall be given to the subject.

13.4. Study Monitoring Requirements

An authorized Sponsor representative will conduct site visits to inspect study data, subjects' medical records, and eCRFs in accordance with ICH guidelines, GCP, and the foreign regulations and guidelines, as applicable. A monitor will be utilized for monitoring ongoing drug accountability and adherence to protocol procedures.

The Investigator will allow representatives of the Sponsor and regulatory authorities to inspect facilities and records relevant to this study.

13.5. Study Completion

The Sponsor requires the following data and materials before a study can be considered complete or terminated:

- Laboratory findings, clinical data, and all special test results from screening throughout the study
- eCRFs (including data queries) properly completed by appropriate study personnel, signed and dated by the Investigator

- Copies of complete drug accountability records (drug inventory log and an inventory of returned or destroyed clinical material)
- Copies of protocol amendments and IRB/IEC approval and notification, if appropriate
- A summary of the study prepared by the Investigator (an IRB/IEC summary letter is acceptable)

End of Study Conduct, for the purpose of clinical trial registries, end of trial notifications to regulatory authorities and IRBs/ECs, will be the latest date on which the last visit in time of any study subject occurs.

14. QUALITY CONTROL AND QUALITY ASSURANCE

Written Standard Operating Procedures (SOPs) will be followed to ensure that the study is conducted, and data are generated, documented (recorded), and reported in compliance with the protocol, GCP, and the applicable regulatory requirements. Quality control will be applied to each stage of data handling. Regular monitoring, as defined in ICH GCP E6(R2), Section 1.38, "The act of overseeing the progress of a clinical trial, and of ensuring that it is conducted, recorded, and reported in accordance with the protocol, SOPs, GCP, and the applicable regulatory requirement(s)", will be conducted throughout the conduct of the study.

As defined in ICH GCP E6(R2), Section 5.18.1, the purpose of monitoring is to verify that:

- Rights and well-being of the human subjects are protected.
- The reported study data are accurate, complete, and verifiable from source documents.
- The conduct of the study is compliant with the currently approved protocol/amendment(s), with GCP, and with the applicable regulatory requirements.
- Monitoring is an integral role in the quality control of a clinical trial and is designed to verify the quality of the study.

To fulfill the Quality Assurance requirements of GCP, audits will be conducted to assess and assure the reliability and integrity of a study's quality control systems and recognized standards.

As defined in ICH GCP E6(R2), Section 5.19, the purposes of an audit are to:

- Ensure subject safety
- Assure compliance to study protocol procedures, regulatory requirements, and SOPs
- Assure data quality

15. PROTECTION OF HUMAN SUBJECTS

This study will be conducted in compliance with the ICH Technical Requirements for Registration of Pharmaceuticals for Human Use E6(R2) Guideline for Good Clinical Practice, the ethical principles of the Declaration of Helsinki, FDA GCP guidelines, and any additional national or IRB/IEC-required procedures.

15.1. Informed Consent

This study will be conducted in compliance with ICH E6(R2) Guideline for Good Clinical Practice pertaining to informed consent. Subjects will give written consent to participate in the study at the first visit, prior to initiation of any study-related procedures, after having been informed about the nature and purpose of the study, participation and termination conditions, risks, and benefits. If a subject is unable to provide written informed consent, the subject's legally acceptable representative (i.e., acceptable to ICH and local law, as applicable) may provide written consent, as approved according to institution-specific guidelines. The ICF must be signed and dated by the subject, or the subject's legally acceptable representative, prior to study participation. A copy of the ICF must be provided to the subject or the subject's legally acceptable representative. If applicable, it will be provided in certified translation for non-English-speaking subjects. Signed ICFs must remain in the subject's study file and be available for verification by Sponsor at any time.

15.2. IRB/IEC Approval

This protocol, the ICF, and all relevant supporting data must be submitted to the IRB/IEC for approval. The protocol, ICF, and any advertisement used to recruit study subjects must be approved by the IRB/IEC. Approval by the IRB/IEC of the protocol and ICF must be obtained before the study may be initiated.

The Investigator is responsible for informing the IRB/IEC of any changes made to the protocol, and to advise them, at least once a year, about the progress of the study. The Investigator is also responsible for notifying the IRB/IEC of any significant AEs that occur during the study.

